1.3 Overall Risk/Benefit Assessment

This phase I/II study will assess the safety, tolerability and efficacy tofacitinib in patients with dcSSc. SSc is one of the most fatal rheumatic diseases, and is associated with substantial morbidity and many detrimental effects on health-related quality of life. There are no FDA approved drugs for SSc.

1.4 Study Rationale

This study will evaluate tofacitinib treatment in subjects 18 to 70 years of age with dcSSc in placebo controlled trial. This phase I/II study is intended to provide safety, and tolerability data in participants with early dcSSc when dosed to target exposures similar to that used in adult participant with RA.

This study will evaluate safety and tolerability, along with descriptive efficacy and pharmacokinetics of tofacitinib as treatment for early dcSSc. After 24 weeks of double blind treatment, participants will then be able to continue into the open label phase during which they will receive tofacitinib 5 mg twice a day for 24 weeks. The primary objective of this study will be to demonstrate acceptable safety and tolerability of tofacitinib in early dcSSc.

1.5 Summary of Rationale for the Proposed Study

Tyrosine kinase inhibitors have been proposed as logical targets for novel treatment strategies in SSc¹, but not much attention has yet been given to the possible use of JAK inhibitors in SSc. However, the various considerations noted above regarding the pathogenesis of SSc and the target effects of tofacitinib provide a compelling case for *in vitro*, animal model and human clinical testing of this agent in SSc. The ability of tofacitinib to suppress both Th2 differentiation and the pro-fibrotic effects of Th2 cytokines, while sparing Treg function is a combination of effects that may make this drug especially suitable for SSc.

1.6 Dose Rationale

The doses of tofacitinib to be evaluated within this study are selected based on the regulatory approval for RA. We plan to administer tofacitinib at 5 mg twice daily (BID), an approved dose of tofacitinib in adult RA patients in most countries.

2. STUDY OUTCOMES

2.1 Primary Outcomes

The **primary study endpoint** will be the proportion of participants who experience Grade 3 (severe) or higher adverse events that occur at or before Week 24.

2.2 Secondary Outcomes

The **secondary study endpoints** will include:

- Number of Grade 3(severe) or higher adverse events that occur at or before Weeks 12, 36, and 48

- Number of Grade 2 (moderate) or higher adverse events that occur at or before Weeks 12, 24, 36, and 48
- Number of AE's of special interest (AESI) at Weeks 12, 24, 36, and 48
- Change in modified Rodnan Skin Score (mRSS) at Weeks 12, 24, 36, and 48
- Provisional American College of Rheumatology Combined Response Index in Systemic Sclerosis at Weeks 12 , 24, and 48.

2.3 Exploratory Outcomes

To assess the efficacy of treatment using 5mg of tofacitinib versus placebo. These **exploratory study endpoints** will include any change in the following scores at the following time points highlighted below.

- Proportion of subjects with mRSS improvement of 20%, 40%, and 60% at weeks: 12 and 24
- Comparison of average, most representative, and maximum skin score methodology for mRSS
- Physician's global assessment on a Likert scale at weeks: 12, 24,36 and 48
- Patient's global assessment on a Likert scale at weeks: 12, 24,36 and 48
- Health-related quality of life (HRQOL) using PROMIS-29 2.0 at weeks: 12, 24,36 and 48
- Physical function as assessed by the scleroderma health assessment questionnaire-disability index (SHAQ-DI) at weeks: 12, 24,36 and 48
- Gastrointestinal symptoms as assessed by UCLA SCTC GIT 2.0 at weeks: 12, 24,36 and 48
- Scleroderma-related skin symptoms assessed by PRO-SRSS at weeks: 12, 24, 36 and 48
- Percent predicted FVC at weeks: 12, 24, and 48
- Change in left ventricular ejection fraction at week 24
- Change in tricuspid regurgitation jet at week 24

3. REGULATORY OBLIGATIONS

3.1 Good Clinical Practice

This study will be conducted in accordance with Good Clinical Practice (GCP), as defined by the International Conference on Harmonization (ICH) and in accordance with the ethical principles underlying European Union Directive 2001/20/EC and the United States Code of Federal Regulations, Title 21, Part 50 (21CFR50).

The study will be conducted in compliance with the protocol. The protocol, any amendments, and the participant informed consent will receive Institutional Review Board/Independent Ethics Committee (IRB/IEC) approval/favorable opinion before initiation of the study.

Study personnel involved in conducting this study will be qualified by education, training, and experience to perform their respective tasks. This study will not use the services of

study personnel where sanctions have been invoked or where there has been scientific misconduct or fraud (e.g., loss of medical licensure; debarment).

3.2 Institutional Review Board

The investigator must have written and dated approval/favorable opinion from the IRB for the protocol, consent form, participant recruitment materials/process (e.g., advertisements), along with any other written information that is planned to be provided to participants, prior the initiation of the study.

The investigator should provide the IRB/IEC with reports, updates, and other information (e.g., expedited safety reports, amendments, and administrative letters) according to regulatory requirements or local institution procedures.

3.3 Informed Consent

The investigator, or a person designated by the investigator, will obtain written informed consent from each subject or the subject's legally acceptable representative, before any study-specific activity is performed, unless a waiver of informed consent has been granted by an IRB/EC. The investigator will retain the original of each subject's signed consent document.

The rights, safety, and well-being of the study participants are the most important considerations and should prevail over interests of science and society.

3.4 Confidentiality

[figure not shown]
The Investigator must ensure that the subject's confidentiality is maintained. On the case report forms or other documents submitted to the Sponsor or designee, subjects should be identified by unique initials and a subject study number only. Documents that are not for submission to the Sponsor or designee (e.g., signed informed consent/assent forms) should be kept in strict confidence by the Investigator.

4. INVESTIGATIONAL PLAN

4.1 Study Design and Duration

This is a phase I/II placebo controlled study to evaluate the efficacy, safety, and tolerability, and pharmacokinetics of tofacitinib as a treatment for early dcSSc. The study will enroll approximately 15 Subjects from 18 to 70 [inclusive] years of age with active dcSSc. Subjects will be randomized to tofacitinib vs. placebo in a 2:1 ratio at 5 mg twice a day for 24 weeks. Subjects will be able to continue into the open label phase during which they will receive tofacitinib 5 mg twice a day for 24 weeks. There will be also be a follow up phone call which will occur 30 days post completing/discontinuing study medication. This study will be conducted over a period of approximately 2 years. Two sites are expected to participate in this study.

4.2 Study Schema

4.3 Study Population

This study can fulfill its objectives only if appropriate subjects are enrolled. The following eligibility criteria are designed to select subjects for whom participation in the study is considered appropriate. All relevant medical and nonmedical conditions should be taken into consideration when deciding whether a particular subject is suitable for this protocol. Subjects will be able to participate with this study drug in combination with methotrexate or other non-biologic immunosuppressive agents.

4.4 Inclusion Criteria

Subjects must meet all of the following inclusion criteria to be eligible for enrollment in the study:

1. Diagnosis of SSc, as classified using the 2013 American College of Rheumatology/ European Union League Against Rheumatism classification of SSc⁵¹.
2. dcSSc as defined by 2001 LeRoy and Medsger⁵²
3. Disease duration ≤ 60 months (defined as time from the first non-Raynaud phenomenon manifestation)
4. mRSS units ≥ 10 and ≤ 45 at screening.
5. Agreement to receive varicella-zoster vaccination or have received vaccination prior to screening.
6. Oral corticosteroids (≤ 10 mg/day of prednisone or equivalent) are permitted if the patient is on a stable dose regimen for ≥ 2 weeks prior to and including the baseline visit.
7. PDPE-5 inhibitors for Raynaud's and digital ulcers are permitted to use as oral monotherapy
8. Age ≥ 18 years and ≤ 70 years
9. Ability to provide informed consent.

4.5 Exclusion Criteria

Subjects with any of the following characteristics/conditions will not be included in the study:

1. Rheumatic disease other than dcSSc; it is acceptable to include patients with fibromyalgia, Sjogren syndrome, and scleroderma-associated myopathy
2. Limited cutaneous SSc or sine scleroderma
3. Significant trauma or major surgery (including joint surgery) within 8 weeks prior to baseline.
4. Any infected ulcer at screening
5. Subjects with any serious bacterial infection within the last 3 months, unless treated and resolved with antibiotics, or any chronic bacterial infection (e.g., chronic pyelonephritis, osteomyelitis, or bronchiectasis)
6. Oral corticosteroids >10 mg/day of prednisone or equivalent.
7. Treatment with anti-CD20 6 months prior to baseline and/or B cell counts less than the lower limit of normal
8. Hydroxychloroquine >400 mg/day, methotrexate >25 mg/week, D-Penicillamine >1000mg/day or mycophenolate mofetil > 2 grams/day prior to baseline. **Subjects can be on combination therapy of hydroxychloroquine and methotrexate or hydroxychloroquine and mycophenolate mofetil and must have been on a stable dose for at least 1month prior to baseline visit.
9. Prior history of treatment in the 3 months prior to baseline with biological DMARDs potent immunosuppressants such as cyclosporine and azathioprine
10. Treatment with etanercept within ≤ 2 weeks of baseline: infliximab, certolizumab, golimumab, abatacept, tocilizumab, or adalimumab within ≤ 8 weeks of baseline; and anakinra within ≤ 1 week prior to the baseline visit.
11. Intravenous corticosteroids within 2 weeks prior to baseline visit.
12. Treatment with any investigational agent ≤ 4 weeks prior to baseline (or 5 half-lives of the investigational drug, whichever is longer)
13. Other investigational or marketed biologics with immunomodulatory properties within 3 months prior to baseline.
14. Any prior treatment with cell-depleting therapies other than anti-CD20 such as CAMPATH, anti-CD4, anti-CD5, anti-CD3, anti-CD19
15. Any prior treatment with chlorambucil, bone marrow transplantation, or total lymphoid irradiation
16. Vaccinated or exposed to a live/attenuated vaccine (other than Zostavax/Shingrix®) ≤ 6 weeks prior to baseline; or is expected to be vaccinated or to have household exposure to these vaccines during treatment or during the 6 weeks following discontinuation of study medication. (**See additional inclusion for obtaining Zostavax/Shingrix® prior to entering the study)
17. Pulmonary disease with FVC $\leq 50\%$ of predicted, or DLCO (uncorrected for hemoglobin) $\leq 40\%$ of predicted
18. History of pulmonary arterial hypertension (PAH) with mean PAP > 30 mmHg on right heart catheterization requiring subcutaneous or intravenous prostacyclin or dual use of oral PAH therapies
19. Subjects at risk for tuberculosis (TB).
 - A. Specifically excluded from this study will be participants with a history of active TB within the last 3 years, even if it was treated; a history of active TB greater than

3 years ago, unless there is documentation that the prior anti-TB treatment was appropriate in duration and type; current clinical, radiographic, or laboratory evidence of active TB; (TB results within 30 days of screening will be accepted and will not to be repeated.

B. Latent TB at or within 30 days of screening, history of or current positive purified protein derivative tuberculin skin test (PPD) ($> 5\text{mm}$ induration, regardless of Bacille Calmette Guerin [BCG] vaccine and/or QuantiFERON Gold, a negative chest x-ray, and no symptoms or risk factors), unless one month of prophylaxis has been completed prior to inclusion

- An indeterminate QuantiFERON® unless followed by a subsequent negative PPD or negative QuantiFERON® or a consultation with and clearance by local infectious disease (ID) department is required.

20. Positive for hepatitis B surface antigen at or within 30 days of screening
21. Positive for hepatitis C antigen at or within 30 days of screening
22. Current or recent history of uncontrolled clinically significant renal, hepatic, hematologic, gastrointestinal, metabolic, endocrine, pulmonary, cardiac or neurologic disease.
23. History of HIV (as determined by medical records or patient reported).
24. History of diverticulitis or chronic, ulcerative lower GI disease such as Crohns disease, ulcerative colitis, or other symptomatic, lower GI conditions that might predispose a patient to perforations.
25. Pregnant or breastfeeding female subjects; and female subjects of childbearing potential who are unwilling or unable to use a highly effective method of contraception as outlined in the protocol for the duration of the study and for at least 28 days after discontinuation of study drug.
26. Severe acute or chronic medical or psychiatric condition or laboratory abnormality that may increase risk associated with study participation and in the judgment of the investigator would make the subject inappropriate for entry into this study.
27. History of SSc Renal Crisis within the 6 months prior to baseline.
28. Any of the following lab results at screening:^a
 - Hemoglobin $<9\text{ g/dL}$ or Hematocrit $<30\%$
 - White Blood Cell count $<3.0 \times 10^9/\text{L}$;
 - Absolute Neutrophil count $<1.2 \times 10^9/\text{L}$;
 - White Blood Cell count $<3.0 \times 10^9/\text{L}$;
 - Absolute Neutrophil count $<1.2 \times 10^9/\text{L}$;
 - Platelet count $<100 \times 10^9/\text{L}$;
 - Absolute Lymphocyte count $<0.75 \times 10^9/\text{L}$.
 - ALT or AST $> 1.5 \times$ the upper limit of normal (ULN) of normal at screening or any uncontrolled clinically significant laboratory abnormality that would affect interpretation of study data or the patient's participation in the study
 - Total bilirubin $> \text{ULN}$ at Screening.
 - Estimated glomerular filtration rate [GFR] $<40\text{mL/min}/1.73\text{ m}^2$

29. History of recurrent (more than one episode) herpes zoster or disseminated (at least one episode) herpes zoster, or disseminated (at least one episode) herpes simplex
30. History of any lymphoproliferative disorder, such as Epstein Barr Virus (EBV) related lymphoproliferative disorder, history of lymphoma, leukemia, or signs and symptoms suggestive of current lymphatic disease.
31. History of any malignancy in the last 5 years with the exception of adequately treated or excised basal cell or squamous cell or cervical cancer in situ.
32. History of alcohol or substance abuse, unless in full remission for greater than 6 months prior to first dose of study drug.

^a Please note thresholds for lab parameters indicated throughout this protocol can differ from the published, current package insert due to a new disease and concomitant immunosuppressive therapies.

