WOCBP must have a negative serum or urine pregnancy test result (minimum sensitivity 25 IU/L or equivalent units of HCG) within 0 to 48 hours before the first dose of study drug. Women must not be breast-feeding.

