All participants who have not received Zostavax® prior will follow the timeline indicated below considering whether or not they are on background immunosuppressive therapy. Participants currently on background therapy (i.e.: methotrexate, mycophenolate, D-Penicillamine) will be asked to temporarily hold these medications for 14 days, receive Zostavax®, wait another 14 to re-start the background medication and then 28 days later can continue on to randomization. If the participant is on mycophenolate mofetil at > 2grams/day (if on Mycophenolic acid prior, must be re-started ≤ 1440 mg/day) at the screening visit, the mycophenolate will need to be started at ≤ 2 grams/day. Participants on stable, acceptable criteria dosages of hydroxychloroquine as background therapy are not required to interrupt their background therapy and can follow the same timeline indicated for those not on background immunosuppressive therapy. Participants not on background immunosuppressive therapy will only have to wait for 14 days post vaccination to be randomized.

Possible screening timelines:

1. Screening → Participant had Zostavax → continue to randomization after criteria is confirmed
2. Screening → Participant is not on background therapy (or is on stable hydroxychloroquine) but requires Zostavax → confirm criteria and participant obtains Zostavax → randomization may occur 14 days post vaccination
3. Screening → Participant is on a background therapy that requires interruption for vaccination → Confirm eligibility, temporarily hold the medications for 14 days → Receive the Zostavax → Re-start at eligible doses (ensuring ≤ 2 grams mycophenolate/ methotrexate ≤ 25) 14 days post vaccination → ensure stable dosing by waiting an additional 28 days → Randomization (up to 65 day window).

Participants can also enter the study having received the Shingrix vaccine. If both doses of Shingrix have been received the participant may start screening and may randomize as long as 4 weeks have passed since receiving the 2nd dose. Alternatively, a participant can begin screening with only one dose if they will be receiving the 2nd dose and can complete the 4 weeks waiting period prior to randomization and still staying within the window.

The screening window will be up to 65 days to ensure these steps are all completed.

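### Laboratory entry limits are tested only at screening, up to 65 days before first dose; the Baseline CBC and panel need a pre-dispensing review, and two laboratory AESIs need a pre-dose reference value

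*Protocol*

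**What the plan says.** Protocol section 4.5, exclusion 28, rules out subjects with "Any of the following lab results at screening". It then gives numeric limits for hemoglobin or hematocrit, WBC, ANC, platelets, lymphocytes, ALT/AST, total bilirubin and GFR. Under the same screening heading, the ALT/AST bullet adds a catch-all for "any uncontrolled clinically significant laboratory abnormality that would affect interpretation of study data".

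Section 4.7.1 states: "The screening window will be up to 65 days to ensure these steps are all completed". Footnote a to the schedule in 6.1 gives the same window. For unvaccinated subjects on background therapy that must be interrupted for Zostavax, the third screening timeline in 4.7.1 starts with "Confirm eligibility, temporarily hold the medications for 14 days". Vaccination, restart and a stable-dose wait follow.

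The 6.1 schedule marks Eligibility Review at Screening only. It marks CBC and comprehensive panel at both Screening and Baseline, and first dispensing of study drug at Baseline.

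For AESIs, section 7.5.1 measures laboratory abnormalities against the screening value, at any time point, with confirmation by repeat. SAP 1.2.3 counts AESIs up to Weeks 12 and 24 and does not require onset after first dose. The notes to SAP Listings 3 and 4 define treatment-emergent events as those starting after first dose.

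**The concern.** Entry limits protect subjects when exposure begins, but here they are tested at a visit that may be about two months earlier. On the hold-and-restart route the gap also contains a planned change in immunosuppressive treatment. A subject whose ALT, platelets or GFR has crossed the sponsor's own limit since screening still satisfies exclusion 28 as written. Blood that would show this is drawn at the dispensing visit, yet no step makes anyone compare it with the limits before drug is handed out. The stake is patient safety in a trial whose objective is acceptable safety and tolerability.

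The second, smaller matter is analytic. If laboratory AESIs are measured from screening, a change that was complete before first dose can be counted as an on-study event.

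**Working it through.** **1. Age of the qualifying results at first dose.** Inputs are the 65-day window (4.7.1 and 6.1) and the route steps in 4.7.1.

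| Route | Minimum interval | Maximum |
|---|---|---|
| Timeline 1: Zostavax already received | none stated | 65 days |
| Timeline 2: Zostavax needed, no therapy to hold | 14 days after vaccination | 65 days |
| Timeline 3: therapy held for Zostavax | 14 (hold) + 14 (vaccine to restart) + 28 (stable dose) = 56 days | 65 days |

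On timeline 3, eligibility is confirmed before the hold begins. The qualifying results are therefore 56 to 65 days old and were taken before the interruption and restart. The slack for any repeat is 65 − 56 = 9 days. Subjects using Shingrix follow a separate rule (4 weeks after the second dose) and do not go through the hold.

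**2. What acts on the Baseline CBC and panel before dispensing.** Each candidate safeguard, with what it does and does not require:

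- Section 5.2: the investigator verifies eligibility before randomization. For exclusion 28, the criterion being verified is the screening value.
- Exclusion 22: "Current or recent history of uncontrolled clinically significant renal, hepatic, hematologic" and other organ disease. It has no screening time stamp, but is non-numeric.
- Exclusion 26: "laboratory abnormality that may increase risk associated with study participation", in the investigator's judgment. It is also untimed and non-numeric.
- Section 4.8: mandatory discontinuation for a laboratory abnormality, on the investigator's opinion.
- Section 7.8: a blinded lab monitor reviews subject labs, with numeric rules for reducing or stopping drug. No review is tied to the time before first dose, and the rules are not entry criteria.

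None of the five is a numeric check on the Baseline draw before dispensing. Section 4.6 shows how the protocol words such a check when it wants one: the pregnancy test must be negative "within 0 to 48 hours before the first dose of study drug".

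**3. The AESI reference value.** Take an illustrative subject with hemoglobin 14.0 g/dL at screening, 11.9 at Baseline and 11.9 on treatment.

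- Drop from screening: 14.0 − 11.9 = 2.1 g/dL. This exceeds 2 g/dL, so it is an AESI under 7.5.1 if confirmed.
- Drop from the last pre-dose value: 11.9 − 11.9 = 0 g/dL, so there is no event.

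The Baseline value of 11.9 is well above the 9 g/dL entry limit, so re-checking eligibility would not remove this case. It needs its own correction. Because the shift happens before any study drug is taken, it does not depend on arm.

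**The case against.** The case on the other side has real weight.

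- **Judgment safeguards exist.** Section 5.2 makes randomization wait for verified eligibility, exclusions 22 and 26 apply at that point, and a blinded monitor reads the labs. An attentive investigator who sees a bad Baseline result has the authority to withhold drug. This stands. What is missing is a requirement to look before dispensing, and a number to look against.
- **Exclusion 28 is not an outlier.** A reader might infer that it was timed carelessly because many other exclusions count back from baseline. Those are mainly washouts, dose limits and recent-event look-backs such as "History of SSc Renal Crisis within the 6 months prior to baseline", for which baseline is the natural anchor. Criteria that rest on an examination or test are often tied to screening: mRSS (inclusion 4), infected ulcer (exclusion 4), latent TB and hepatitis (exclusions 19 to 21). Exclusion 28 follows that pattern.
- **The 7.8 thresholds are a different matter.** A reader might take their being looser than the entry limits, or covering fewer parameters, as part of the defect. Stopping rules serve another purpose and may properly be looser. Nothing here argues for changing them.
- **Week 6 is not a blind interval.** It is the next scheduled draw after Baseline, but the Baseline results are safety labs from the local laboratory and fall under 4.8 and 7.8 once reported. The documents do not suggest that they go unread.
- **The AESI wording has partial cover.** Section 7.1 defines an adverse event in a participant given product, and 7.7 starts non-serious collection at initiation of study drug. However, 7.6 calls for collection of adverse events from consent, and 7.5.1 names screening as the reference. The ambiguity remains.
- **A second check has a price.** In a 15-subject trial, a small excursion such as bilirubin just above ULN could cost a subject who has already held therapy and been vaccinated. This is why a repeat should be allowed.

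**Conclusion.** The point holds as a modest, inexpensive improvement. The numeric entry limits are tested once, up to 65 days before first dose, and at least 56 days before it on the Zostavax hold-and-restart route. The Baseline results that could update them carry no limit and no required pre-dispensing review.

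The 56-day figure applies to a subgroup whose size the documents do not give: unvaccinated, on methotrexate, mycophenolate or D-penicillamine, and using Zostavax. How often values cross a limit in the interval is also not given, so no harm rate can be stated. Sites may repeat labs on their own initiative, but the text does not require it.

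The AESI reference is a separate, smaller point. It adds noise to a secondary endpoint. A chance imbalance between 10 and 5 subjects is possible, but there is no systematic bias between arms. A reader might infer that the primary comparison of Grade 3 or higher events is compromised; nothing in the documents supports that.

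**What to change.** **Fix 1 (patient safety).** Add to exclusion 28 or section 5.2: *The most recent CBC and comprehensive panel before first dose are reviewed against the limits in exclusion 28 before study drug is dispensed. A value outside a limit may be repeated once within the 65-day window; study drug is not given if the repeat is also outside the limit.* Mark Eligibility Review at Baseline in 6.1 and leave the limits unchanged. The review is best done before randomization, because a subject randomized but never dosed falls outside both analysis sets in SAP 2.1.

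Cost: no new test. The Baseline draw can be used, or taken a few days earlier, which may mean an extra trip. Expect a short dispensing delay and an occasional late screen failure; one subject is 1/15 = 6.7% of accrual and would need replacing. On the hold-and-restart route at most 9 days remain for the repeat, so the draw should not be left to the last day of the window.

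**Fix 2 (secondary endpoint).** In section 7.5.1 and SAP 1.2.3, use the last pre-dose value as reference for the hemoglobin-drop and creatinine-rise AESIs. Do not count as on-treatment any laboratory AESI already present before first dose. Lipids are not drawn at Baseline, so the lipid item keeps its screening reference. Cost: about a sentence in each document; screening and Baseline values for hemoglobin and creatinine are already in SAP Table 33.
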